As of 30 June 2013, a total of 25 non-HCC patients who received dovitinib treatment had post-baseline LFT elevations defined as total bilirubin  $> 2 \times$  ULN and AST and/or ALT  $> 3 \times$  ULN (including 1 patients whose LFT increase occurred more than 30 days after the last dose of dovitinib). None of the patients qualifies as a

“Hy’s Law” case (Reuben, 2004). Please see IB edition 12 Section 5.2.1.5 Hepatic dysfunction as defined by laboratory criteria for more detail.

Two cases of hepatic disorders that were deemed dovitinib-related by the Investigator and resulted in death have been reported as of 10 November 2013. Please see IB edition 12 Section 5.2.1.7 Investigator notifications for more detail.

As reported in IB edition 12, baseline and on-study ECG data were available from 854 patients who were treated with TKI258 on the 5 days on / 2 days off schedule across 8 single agent studies, CTKI258A2107, CTKI258A2112, CTKI258A2116, CTKI258A2128, CTKI258A2201, CTKI258A2202, CTKI258A2204, and CTKI258A1101, and one randomized controlled study, CTKI258A2302. Consistent with the September 2009 analyses, outlier analyses did not suggest an effect of dovitinib on the ECG intervals QTcF, PR, or QRS. The proportion of patients with post-baseline QTcF > 480 msec and QTcF > 500 msec were < 1% for each category; the proportion of patients with QTcF change from baseline > 60 msec also was < 1%. Similarly, proportion of patients with notable changes in QRS (increase from baseline > 25% and to a value > 110 msec) and PR (increase from baseline > 25% and to a value > 200 msec) was < 1% for each interval.

As reported in IB edition 12, baseline and on-study cardiac imaging data were available from 527 patients treated with dovitinib across 13 studies: CTKI258A2101, CTKI258A2102, CTKI258A2103, CTKI258A2104, CTKI258A2105, CTKI258A2107, CTKI258A2112, CTKI258A2116, CTKI258A2128, CTKI258A2201, CTKI258A2202, CTKI258A2204, and CTKI258A2302.

Of these 527 patients who had both baseline and on-study data, 20 patients (3.8%) had a post-treatment decrease in ejection fraction (EF)  $\geq 20\%$  on ECHO or MUGA. Among these 20 patients, 15 had EF decrease to a value that was below 50% (Table 5-24). The LVEF data and associated clinical data were reviewed by an independent cardiologist consultant. According to his assessment, dovitinib was probably or at least possibly contributory to the decrease in LVEF in 2 cases, based on the available data.

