## 6.1.4 Treatment Interruption and Treatment Discontinuation

Toxicity intensity a	Dose modification b, c
Cardiovascular	
Hypertension	Treatment-emergent hypertension should be treated as per standard cardiology practice. Recommended agents for the management of blood pressure elevations on dovitinib include angiotensin-converting enzyme inhibitors and calcium channel blockers.
SBP < 160 mmHg and/or DBP < 100 mm Hg, with or without anti-hypertensive medication	Maintain dose level
SBP ≥ 160 mmHg and/or DBP ≥ 100 mm Hg, with or without anti-hypertensive medication, but not immediately life-threatening	Delay the study treatment and initiate/intensify antihypertensive therapy. Dovitinib may be restarted in conjunction with standard anti-hypertensive medication if BP is controlled (i.e. BP < 160/100 mmHg). Once BP is controlled after suspending dovitinib, maintain dose level or ↓ 1 dose level at the discretion of the investigator.
Life-threatening consequences (e.g., malignant hypertension, transient or permanent neurologic deficit, hypertensive crisis); urgent intervention	Discontinue study treatment permanently

Toxicity intensity a	Dose modification b, c
indicated	
Left ventricular systolic dysfunction	
Left ventricular ejection fraction (LVEF) $\geq$ 50%/LLN (ECHO), or $\geq$ 45%/LLN (MUGA)	Maintain dose level
LVEF $<$ 50%/LLN (ECHO), or $<$ 45%/LLN (MUGA), or Symptomatic due to drop in ejection fraction responsive to intervention	Delay study treatment until resolved to $\geq$ 50%/LLN (ECHO) or $\geq$ 45%/LLN (MUGA), then $\downarrow$ 1 dose level
Refractory or poorly controlled heart failure due to drop in ejection fraction; intervention such as ventricular assist device, intravenous vasopressor support or heart transplant indicated	Discontinue study treatment
Other cardiovascular	
Grade 1	Maintain dose level
Grade 2	Maintain dose level If asymptomatic decrease of LVEF by absolute value of 20% and to $<$ LLN, delay study treatment until resolved to $\leq$ grade 1, then $\downarrow$ 1 dose level
Grade 3	Delay study treatment until resolved to $\leq$ grade 1, then $\downarrow$ 1 dose level
Grade 4	Discontinue study treatment
Gastrointestinal	
Diarrhea	At the first sign of abdominal cramping, loose stools, or onset of diarrhea, it is recommended that the patient be treated according to institutional standard of care
Grade 1 (despite maximal anti-diarrheal medication)	Maintain dose level

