Grade 3	Delay study treatment until resolved to ≤ grade 1, then: If resolved by ≤ 7 days after suspending dovitinib, maintain dose level If resolved by > 7 days after suspending dovitinib, ↓ 1 dose level
Grade 4	Delay study treatment until resolved to ≤ grade 1, then ↓ 1 dose level
Hepatic	
≥ grade 3 alkaline phosphatase or GGT	Isolated values of ≥ grade 3 alkaline phosphatase or GGT values will NOT require dose interruption.
ALT or AST	
≤ 3.0 x ULN	Maintain dose level with LFTs e monitored as per protocol.
> 3.0 to ≤ 5.0 x ULN, without bilirubin elevation to > 2.0 x ULN	Maintain dose level with weekly monitoring of LFTs e , or more frequently if clinically indicated, until resolved to ≤ grade 1 or baseline.
> 5.0 x ULN	Delay study treatment until resolved to ≤ grade 1 or baseline, then ↓ 1 dose level. Monitor LFTs e weekly, or more frequently if clinically indicated, for 8 weeks; then, every 2 weeks for 4 weeks; then, every 4 weeks as per protocol. Following re-introduction of dovitinib, if ALT or AST elevations > 3 x ULN recur as assessed on 2 separate measurements no more than 1 week apart, then study treatment should be permanently discontinued. If study treatment is permanently discontinued, then patients should be monitored weekly (including LFTs e ), or more frequently if clinically indicated, until AST or ALT have resolved to ≤ grade 1 or stabilization (i.e., no CTCAE grade change over 4 weeks).
Total bilirubin	
≤ 1.5 x ULN	Maintain dose level with LFTs e monitored as per protocol.
> 1.5 to 3.0 x ULN with ALT or AST ≤ 3.0 x ULN	Maintain dose level with LFTs e monitored as per protocol.

Toxicity intensity a	Dose modification b, c
> 3.0 x ULN	
Discontinue study treatment permanently.
 
Patients should be monitored weekly (including LFTse), or more frequently if clinically indicated, until total bilirubin has resolved to ≤ grade 1 or stabilization (i.e., no CTCAE grade change over 4 weeks).
 
Note: If grade 3 or grade 4 hyperbilirubinemia is due to the indirect component only, and hemolysis as the etiology has been ruled out as per institutional guidelines (e.g., review of peripheral blood smear and haptoglobin determination), then ↓ 1 dose level and continue treatment at the discretion of the investigator.

ALT or AST, and concurrent Bilirubin elevation	

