ALT or AST > 3.0 x ULN AND Total Bilirubin > 2.0 x ULN	
Discontinue study treatment permanently.
 
Patients should be monitored weekly (including LFTse), or more frequently if clinically indicated, until ALT/AST and total bilirubin have resolved to ≤ grade 1 or stabilization (i.e., no CTCAE grade change over 4 weeks).

Renal	
Serum creatinine	
Grade 1 or 2	Maintain dose level
Grade 3	Delay study treatment until resolved to ≤ grade 1 or baseline, then ↓ 1 dose level
Grade 4	Discontinue study treatment
Amylase and/or lipase elevations	
Asymptomatic Grade 1 or 2	Maintain dose level
Asymptomatic Grade 3 or 4	Patients who develop grade 3 or 4 hyperlipasemia or hyperamylasemia without clinical or other evidence of pancreatitis may continue study medication without interruption
Pancreatitis	
Grade 2	Maintain dose level
Grade 3 or 4	Discontinue study treatment
Hand-foot syndrome	
Grade 1 or 2	Maintain dose level
Grade 3	Delay study treatment until resolved to ≤ grade 1 then ↓ 1 dose level
Grade 4	Discontinue study treatment
Other clinically significant adverse events	
Grade 1 or 2	Maintain dose level
Grade 3 (except hyperlipidemia d )	Delay study treatment until resolved to ≤ grade 1 or baseline, then maintain dose level or ↓ 1 dose level at the discretion of the investigator
Grade 4	Delay study treatment until resolved to ≤ grade 1 or baseline, then ↓ 1 dose level or discontinue dovitinib at the discretion of the investigator
All dose modifications should be based on the worst preceding toxicity.	
a Common Terminology Criteria for Adverse Events (CTCAE) v4.03	
b Patients are allowed two dose reductions: a dose reduction to 400 mg from 500 mg, and, if necessary, a dose reduction to 300 mg from 400 mg.	
c If a patient requires a dose interruption of > 14 days starting from the first day a dose was missed, then the patient must be discontinued from the study. Patients who discontinue the study for a study related adverse	

Toxicity intensity a	Dose modification b, c
event including an abnormal laboratory value must be followed at least once a week for 4 weeks and subsequently at 4 week intervals until resolution or stabilization of the event, whichever comes first.	

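### Rows of the Section 6.1.4 dose-modification table overlap for liver tests and blood pressure, so one set of values can call for different actions, and no precedence is stated.

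*Combined protocol and SAP*

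**What the plan says.** Section 6.1.4 gives an action for each toxicity row. The rows that matter here are these.

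**Liver**
- Transaminases, middle band: "> 3.0 to ≤ 5.0 x ULN, without bilirubin elevation to > 2.0 x ULN". Action: maintain dose, with weekly liver tests.
- Transaminases above 5.0 x ULN, with no condition on bilirubin. Action: "Delay study treatment until resolved to ≤ grade 1 or baseline, then ↓ 1 dose level". The row goes on to describe monitoring and what to do if the elevation recurs after re-introduction.
- Total bilirubin, middle band: "> 1.5 to 3.0 x ULN with ALT or AST ≤ 3.0 x ULN". Action: maintain dose, with routine liver tests.
- Concurrent elevation, under its own sub-heading: "ALT or AST > 3.0 x ULN AND Total Bilirubin > 2.0 x ULN". Action: permanent discontinuation.

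**Blood pressure**
- "SBP < 160 mmHg and/or DBP < 100 mm Hg, with or without anti-hypertensive medication". Action: maintain dose.
- "SBP ≥ 160 mmHg and/or DBP ≥ 100 mm Hg, with or without anti-hypertensive medication, but not immediately life-threatening". Action: delay. Restart is allowed "if BP is controlled (i.e. BP < 160/100 mmHg").

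A line at the foot of the table ties dose modifications to the worst toxicity seen beforehand. The footnote to Table 6-2 (Section 6.1.3) says much the same for dose reductions. Neither says what to do when one set of values meets two rows.

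**The concern.** A dose-modification table works only if a site can take a patient's values to one row and read off one action. Here some values lead to two rows with different actions, and in the liver section the choice is between restarting and stopping for good.

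The hazards are ones the protocol itself names. Section 1.2.2 reports two fatal hepatic disorders that investigators judged related to dovitinib, and lists hypertensive crisis among the dose-limiting toxicities. It sends investigators back to the protocol's own guidance for liver and blood-pressure management, so this table is the operative text. The trial is multi-center (Section 4.1), so two sites that follow the table faithfully could treat identical values differently.

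**Working it through.** The plan states no figure to reproduce. The check writes each row as a logical condition and asks which values satisfy more than one. Liver values are in multiples of ULN and b is total bilirubin.

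**1. Transaminase above 5.0 with raised bilirubin**
- Delay row: max(ALT, AST) > 5.0.
- Permanent-stop row: max(ALT, AST) > 3.0 and b > 2.0.
- Both are met when max(ALT, AST) > 5.0 and b > 2.0.

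This does not depend on how any connector is read. The band just below (> 3.0 to 5.0) avoids the clash because it excludes b > 2.0. The > 5.0 row carries no such exclusion.

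**2. Bilirubin maintain row**
- Literal reading (either transaminase suffices): 1.5 < b ≤ 3.0 and min(ALT, AST) ≤ 3.0.
- Overlap with the permanent-stop row: 2.0 < b ≤ 3.0 and min(ALT, AST) ≤ 3.0 < max(ALT, AST).
- If both transaminases must be ≤ 3.0, the maintain row requires max(ALT, AST) ≤ 3.0. That contradicts max(ALT, AST) > 3.0, so the overlap is empty.

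**3. Blood pressure**
- Literal maintain row: SBP < 160 or DBP < 100.
- Delay row: SBP ≥ 160 or DBP ≥ 100.
- Both are met when SBP ≥ 160 with DBP < 100, or SBP < 160 with DBP ≥ 100.
- If both pressures must be below their limits, the maintain row is exactly the complement of the delay row and the overlap is empty.

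**Test values**

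| Values | Literal reading | Maintain rows require both values |
|---|---|---|
| BP 150/90 | maintain | maintain |
| BP 170/90 | maintain and delay | delay |
| BP 150/105 | maintain and delay | delay |
| BP 170/105 | delay | delay |
| ALT 4, AST 2, b 2.5 | maintain and stop permanently | stop permanently |
| ALT 4, AST 4, b 2.5 | stop permanently | stop permanently |
| ALT 6, AST 2, b 2.5 | maintain, delay and stop permanently | delay and stop permanently |
| ALT 6, AST 6, b 2.5 | delay and stop permanently | delay and stop permanently |

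Overlaps 2 and 3 need discordant values (one of the pair above its limit, the other not) and a literal reading. Overlap 1 needs neither. The right-hand column shows where each conflict comes from. It does not say which action is clinically right.

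**Frequency**

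Section 1.2.2 says that "a total of 25 non-HCC patients who received dovitinib treatment had post-baseline LFT elevations", defined by bilirubin > 2 x ULN with AST and/or ALT > 3 x ULN. It gives no denominator and no split by one or both transaminases, by > 5.0 x ULN, or by bilirubin ≤ 3.0. As an illustration only, two totals from the same section can stand in as denominators: 2078 patients treated, or 1009 with adverse-event and/or laboratory data. Neither is matched to the 25 by date or population.
- 25/2078 = 1.2%, and 0.012 x 20 = 0.24 patients.
- 25/1009 = 2.5%, and 0.025 x 20 = 0.50 patients.

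Only some of these would face a conflict: both transaminases at 4 with bilirubin 2.5 meets one row only. No corresponding figure can be formed for blood pressure.

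**The case against.** The strongest reply is that the intent can be seen. The restart text treats control as being below 160/100. Exclusion 8e in Section 5.2 calls hypertension uncontrolled when either pressure reaches its limit, so 170/90 counts as uncontrolled there. Concurrent liver elevation has its own sub-heading, and the > 3.0 to 5.0 band carves out raised bilirubin. The line on worst preceding toxicity leans toward the stricter row. Section 7.6 lets the treating physician stop dovitinib for toxicity, so no maintain row forces continued dosing. A careful site would probably take the cautious action.

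Much of this stands. It makes overlaps 2 and 3 look like loose drafting and lowers the chance that a site acts on the maintain row. It does not settle the matter. The worst-toxicity line ranks toxicities and does not say which of two rows governs simultaneous values. The Table 6-2 footnote concerns dose reduction, not permanent discontinuation. Physician discretion permits stopping but does not make two sites choose alike. None of these texts removes overlap 1, where the > 5.0 row describes re-introduction in enough detail for a site to follow it in good faith.

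A reader might infer more than the documents support:
- **That the 25 patients, or about 3 of 20, would face conflicting rows.** The second figure would come from the 14.3% hypertension rate in Section 1.2.2 (0.143 x 20 = 2.9). That rate is hypertension of any degree, with no threshold and no systolic/diastolic split. The 25 are not broken down either.
- **That the 6-month complete response rate is distorted.** Each of 20 patients is 5 percentage points (1/20), patients who do not reach the evaluation count as non-responders (Section 10.1), and some early withdrawals are replaced (Section 7.8). But Section 7.7 asks patients who stop treatment to return for tumor assessments, and nothing shows the direction or size of an effect.
- **That the grade 2 vomiting row is another overlap.** Its recurrence step names nausea, as the nausea row does. That is an apparent copying error, not two rows met at once.

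**Conclusion.** The point holds as an internal contradiction in a safety-action table. Overlap 1 (delay and restart lower versus permanent discontinuation) exists on any reading. Overlaps 2 and 3 (maintain versus permanent discontinuation, and maintain versus delay) exist if the connectors are read as printed, and only for discordant values. It would be too strong to say that every conflict sets a maintain row against a stricter one: the firmest case involves no maintain row.

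How often the conflict would arise cannot be estimated from the documents. The liver illustration, on assumed denominators, gives fewer than one patient in 20 before restriction to values that truly conflict. Sample size, power and alpha are unaffected. The reason to act is that identical values can lead to opposite instructions for hazards the protocol names, and the remedy is cheap.

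**What to change.** Reconcile the liver and blood-pressure rows of Section 6.1.4 so that each set of values falls in one row, or state which row takes precedence when two are met. In particular:
- State how the > 5.0 x ULN transaminase row relates to the concurrent-elevation row.
- Replace the ambiguous connectors in the bilirubin and blood-pressure maintain rows with explicit wording (both or either).

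The sponsor's clinical team must decide which action applies to each conflicting set of values. This review proposes none.

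Separately, as an editorial correction, reconcile the recurrence wording of the grade 2 vomiting row with the event that the row covers.

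The cost is a wording amendment to one table and a memo to sites, with no added visits, tests or patients.

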### **6.1.5 Permitted Concomitant Therapy**

Anti-emetic medications are permitted at the treating physician's discretion.

Colony stimulating growth factor (i.e. erythropoietin, darbopoietin, pegfilgrastim) support is permitted at the treating physician discretion.

Full dose anti-coagulation with low molecular weight heparin (i.e. enoxaparin, fondaparinux) is permitted.

The patient needs to notify the investigational site about any new medications he/she takes after the start of the study drug. All medications (other than study drug) and significant non-drug therapies (including physical therapy and blood transfusions) administered after the patient starts treatment with study drug must be recorded in the eCRF.

### **6.1.6 Prohibited Concomitant Therapy**

Full dose anti-coagulation with warfarin is not permitted.

### **6.1.7 Hormonal Contraception Excluded**

Hormonal contraception is not allowed during the study. Women of childbearing potential are required to use two forms of highly effective contraceptives (e.g. male condom with spermicidal; diaphragm with spermicide; intra-uterine device).

## **6.2 Study Drug(s)**

### **6.2.1 Packaging and Labeling**

Dovitinib will be provided as a gelatin capsule or film coated tablet of 100 mg strength . The capsules/tablets will be provided in either blisters or bottles. Dovitinib medication labels will comply with the legal requirements of each country and be printed in the local language. The inactive ingredients for the dovitinib capsules are pregelatinized starch, colloidal silicon dioxide, microcrystalline cellulose, and magnesium stearate.

### **6.2.2 Supply, Receipt and Storage**

The study drug must be stored in a secure area, limited access area. The storage conditions are

described on the medication label. It will be administered only to patients entered into the clinical study, at no cost to the patient, in accordance with the conditions specified in this protocol. The capsules/tablets should be stored according to the label in a secured, limited access area until required.

Investigational pharmacy will maintain accurate records demonstrating dates and amount of study drug shipped, to whom dispensed (patient by patient accounting), and accounts of any study treatment accidentally or deliberately destroyed. At the end of the study, reconciliation must be made between the amount of study drug supplied, dispensed, and subsequently destroyed or returned.

Details are listed in [Table 6-3](#) below.

**Table 6-3 Drug Supply and Storage**

Study drugs	Supply	Storage
Dovitinib	Centrally supplied by Novartis	Please see study drug label

### **6.2.3 Dispensing and Preparation**

Capsules/tablets including instructions for administration are dispensed by study personnel on an outpatient basis.

Patients will be provided with adequate supply of study drug for self-administration at home until at least their next scheduled study visit.

### **6.2.4 Drug Compliance and Accountability**

#### **6.2.4.1 Drug Compliance**

Compliance will be assessed by the investigator and/or study personnel at each patient visit and information provided by the patient and/or caregiver will be captured in the drug accountability form (see SPM). This information must be captured in the source document at each patient visit.

#### **6.2.4.2 Drug Accountability**

The investigator or designee must maintain an accurate record of the shipment and dispensing of study drug in a drug accountability form (see SPM). Drug accountability will be documented. Patients will be asked to return all unused study drug and packaging on a regular basis, at the end of the study or at the time of study drug discontinuation.

### **6.2.5 Disposal and Destruction**

Any unused study dovitinib will be documented and disposed of according to institutional standards. Documentation of the destruction should be recorded on the drug accountability form (see SPM).

### **6.2.6 Other Concomitant medication**

Patients must be instructed not to take additional medications including over-the-counter products and herbal/alternative medications during the study without prior consultation with the

investigator. It is important to avoid concomitant medications that are known to cause hepatotoxicity.

Oral contraceptives are generally metabolized by CYP3A4/2C9, and act also as a moderate inhibitor of CYP1A2, therefore should not be used. Thus, patients who are sexually active and are using oral contraceptives as a method of contraception should change to two highly effective contraceptive methods during the study participation.

Permitted treatments during the study include, but are not limited to the following:

- Pain medication to allow the patient to be as comfortable as possible
- Nutritional support or appetite stimulants (e.g. megestrol)
- Oxygen therapy and blood products or transfusions
- Prophylactic anti-emetics are allowed for patients who, at the discretion of the investigator, have experienced  $\geq$  grade 1 nausea or vomiting.
- Hematopoietic growth factors should be used according to the guidelines established by the American Society of Clinical Oncology (ASCO) or as dictated by local practice. The ASCO guidelines are available [<http://jco.ascopubs.org/cgi/content/full/24/19/3187>]
- The administration of anticoagulation and antiaggregation agents (e.g. eptifibatide, eprosterolet, prasugrel, dipyridamole, fondaparinux) should be allowed except prasugrel, due to its potential drug-drug interaction with dovitinib. Prasugrel is primarily metabolized by the CYP3A4 and CYP2B6 and to a lesser extent by the CYP2C9 and CYP2C19. In vitro study demonstrated that dovitinib is an inducer of CYP2C9 and CYP2C19, co-administration of dovitinib with prasugrel is likely to reduce the exposure of prasugrel. For oral anticoagulants, the upper limit of INR is  $< 1.5$ .
- The administration of androgen deprivation therapy or orchiectomy as part of the definitive treatment for clinically localized prostate cancer or biochemically relapsed non-metastatic (i.e. PSA relapse only) is permitted.

The following concomitant treatments are not allowed during the study:

- Concurrent use of isoniazid, labetalol, trovafloxacin, tolcapone, and felbamate are not permitted, since alternative less hepatotoxic drugs are available to use.
- Concurrent use of other investigational drugs is not permitted.
- The administration of other antineoplastic therapy (e.g. chemotherapy, immunotherapy, targeted therapy, monoclonal antibodies and radiation therapy) is not permitted.
- The administration of anti-androgen therapy (e.g. bicalutamide, flutamide, nilutamide) for the treatment of prostate cancer is not permitted.
- The administration of androgen deprivation therapy or orchiectomy for the treatment of metastatic prostate cancer is not permitted.

